-Due to power limitations we will restrict the number of covariates/independent variables to eight (10 patients/independent variable)(63). Based on suspected prognostic factors for LBP disability (61, 62) and suspected factors associated with serum cytokine levels (64, 65), we will add the following as covariates into the model due to possible confounding: age, leg pain (0-10 NRS), fear avoidance, emotional distress (dichotomized into HSCL-25 $\geq 1,75$ and $< 1,75$), psychiatric comorbidity (yes/no), other specific comorbidity (numerical, one point for each of rheumatoid arthritis, osteoarthritis, Diabetic, Cardiac/pulmonary) and sick leave (categorized into 1. working full time, 2. partial sick leave and 3. complete sick leave / disability pension / unemployed / student/other/unknown). Age, leg pain and fear avoidance will be continuous variables.

For each model we will evaluate:

1. The predictiveness by comparing the multiple correlation coefficient R^2 of the complete model with the R^2 in the model without the independent variable of interest (66).
2. The effect size described in terms of relative change in RMDQ. We will consider effect size $>30\%$ as clinically relevant, which equates approximately to a difference of 4 out of 12.8 (at baseline) RMDQ points.

The following models (1, 2A, 2B, 3, 4A, 4B, 5A, 5B, 5C, 5D, 5E) will differ in choice of independent variable of interest, which will be:

1. Cytokine category group based on cytokine classification group (4 categories of patients, figure 2). Each category of patients will be assessed versus the three other categories combined.
2. Classification variable defined by a Recursive Partitioning analysis using RPART command in R. Relative change in RMDQ from baseline to one-year follow-up will be dependent variable. Only patients nonmissing values in both baseline and one-year follow-up RMDQ score will be included. Stopping conditions will be $\text{maxdepth}=3$ and n_{min} (minimal number of observations in terminal/leaf node)=5. We will use tenfold cross-validation and a complexity parameter of 0,01. We will perform two Recursive Partitioning models that differs only in what variables that are included:

Statistical Analysis Plan for analysis of cytokines as prognostic factors and predictors of antibiotic treatment effect in patients with chronic low back pain and Modic changes (the AIM trial) - - version 1.0

- A. all 39 cytokines

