| 
Hypothesis 2: Serum proinflammatory cytokine levels are associated with change in RMDQ score from baseline to one-year follow-up.
 
Rationale: Serum cytokine levels could be associated with prognosis in patients with low back pain. Low serum IL-6 and high TNF in patients with acute low back pain was associated with worse outcome after 6 months (37). In patients with lumbar radicular pain, increased levels of IL-6 and IL-8 was associated with worse outcome after 12 months follow-up (40). Subgroups ii. and iii. are motivated by their ability to assess different cut-off values of cytokines, which could be important given the possibility that physiological reactivity may require threshold concentrations (67).
 | 
i. Prespecified classification based on cluster analysis (figure 2), giving four categories of patients (pre-defined)
 | 1 |
| | 
ii. Subgroups defined based on data-mining statistical analyses with recursive partitioning of all 39 cytokines (post-defined)
 | 2 A |
| | 
iii. Subgroups defined based on data-mining statistical analyses with recursive partitioning of all 39 cytokines and known prognostic factors for disability: age, leg pain (0-10 NRS), fear avoidance, emotional distress, comorbidity, physical workload, and sick leave (post-defined)
 | 2 B |
| | 
iv. Abnormal cytokine values, based on PCA analysis of healthy controls and patients with MCs (figure 3), dichotomized into normal (inside yellow circle) and abnormal (outside yellow circle) cytokine levels (pre-defined)
 | 3 |
| | 
v. Principal component 1 from PCA analysis 3A of cytokines as predictors of treatment effect (pre-defined)
 | 4 A |
| | 
vi. Principal component 1 from PCA analysis 3B of cytokines as predictors of treatment effect (pre-defined)
 | 4 B |
| | 
Individual cytokines, categorized with cutoffs at 0, 1 and 2 SD above the mean in the healthy control groups (pre-defined)
 | |
| | 
vii. MIF levels
 | 5 A |
| | 
viii. TNFα levels
 | 5 B |
| | 
ix. IL-6 levels
 | 5 C |
| | 
x. IL-8 levels
 | 5 D |
| 
xi. IL-1β levels
 | 5 E | |

Supportive and sensitivity analyses

Supportive analyses:

Calculate Area under ROC curve (AUC), cutoff value, positive predictive value, negative predictive value, sensitivity and specificity (internal validation/assessing performance (70, 71))

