With 30% improvement of RMDQ from baseline to one-year follow-up as the gold standard status (diagnostic variable), we will calculate Area under ROC curve (AUC), cutoff value, positive predictive value, negative predictive value, sensitivity and specificity for each independent variable of main analyses (1, 2A and 2B) as a prognostic variable of interest (test variable). We will consider the same calculations for each independent variable of the additional analyses (3 to 5).

Assess the direct effect of cytokines on relative change in RMDQ score (baseline to 1-year) in the possible case that baseline value of RMDQ mediates any overall/total effect:

For each linear regression model of the main analyses (1, 2A and 2B) we will perform the same analysis including baseline value of RMDQ as a covariate. These models could also be interpreted to provide estimates of the prognostic effect (without causal inference) of cytokines given a specific baseline value, and we can therefore safely ignore the possible problems with bias mentioned above (under Main analyses). We will consider the same sensitivity analysis for each linear regression model of the main analyses (3 to 5).

Assess the effect of cytokines on relative change in RMDQ score (baseline to 1-year) in the placebo group only, in the possible case that that the subgroup predicts treatment effect:

We will consider (depending on results and power), for each linear regression model of the analyses 1, 4 and 5, performing the same analysis including only patients in the placebo group.

Internal validation

We will consider internal validation on any analyses 1 to 5 (depending on results) by using bootstrapping.

Sensitivity analyses:

The following sensitivity analyses will be performed for the main analyses (1, 2A and 2B), and will be considered performed for the main analyses 3 to 5:

Assess the possibility that covariates included in main analyses are non-confounders/mediators:

For each linear regression model of the main analyses 1, 2A and 2B, we will perform unadjusted analysis with relative change in RMDQ from baseline to one-year follow-up as dependent variable, and the same independent variable as used in each respective model (1, 2A and 2B). These unadjusted analyses are recommended as we cannot rule out the possibility that the covariates included in the main analyses could be non-confounders or mediators (72). Each model will be compared to their respective main analysis by assessing R^2 .

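### Analyses 2A and 2B: ROC figures from the same patients who grew the tree are filed under internal validation, while resampling validation is optional and depends on the results

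*SAP*

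**What the plan says.** All references are to the SAP, hypothesis 2 (cytokines as prognostic factors).

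- **How the tree is grown** (Main analyses, model 2). The outcome and the patients are fixed by "Relative change in RMDQ from baseline to one-year follow-up will be dependent variable. Only patients nonmissing values" at both time points. Depth is limited to 3 and the leaf size by "minimal number of observations in terminal/leaf node)=5". The remaining control is "We will use tenfold cross-validation and a complexity parameter of 0,01". Nothing says whether the cross-validation prunes the tree, or by which rule.
- **What is reported on it** (Supportive analyses). The heading lists AUC, cut-off and "positive predictive value, negative predictive value, sensitivity and specificity (internal validation/assessing performance (70, 71". The reference standard is "With 30% improvement of RMDQ from baseline to one-year follow-up as the gold standard status (diagnostic variable". The figures are mandatory "for each independent variable of main analyses (1, 2A and 2B) as a prognostic variable of interest (test variable" and only to be considered for analyses 3 to 5. No separate data, resampling or rule for choosing the cut-off is named.
- **Validation by resampling** (Internal validation). The whole provision is "We will consider internal validation on any analyses 1 to 5 (depending on results) by using bootstrapping".

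**The concern.** In 2A and 2B the reference standard is the tree's own outcome cut into two classes, in the same patients. The tree has already searched 39 cytokines, each with nine cut-offs, for whatever separates those patients best. Any AUC computed on them describes fit. It does not show how the classification would perform in new patients.

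The only step that could show the difference has no stated trigger. Elsewhere the SAP does give triggers: a difference of more than 4 RMDQ points for the independence check under hypothesis 1, and statistical significance for the one under hypothesis 2. Here the decision to validate can be taken after the AUC has been seen.

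At stake is a published cut-off with predictive values for a cytokine classification, read as internally validated when it is not.

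**Working it through.** **1. The plan's own figures.** The SAP states no AUC or optimism figure. Its hypothesis 2 power statements reproduce:

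- Model 1, n = 28 and 44, difference 4, SD 5. Noncentrality = (4/5) × √(28×44/72) = 0.8 × 4.137 = 3.31 on 70 df, power 0.904 (stated 90%). With exactly 30% of 12.8 = 3.84 points, power is 0.880.
- R² rising from 30% to 37%, n = 78. λ = 78 × 0.07/(1 − 0.37) = 8.67 on 1 and 69 df, power 0.827. Power of 80% is reached at about 6.6 points, which rounds to the stated 7.

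**2. Inputs from the SAP.**

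- Patients with RMDQ at both times: 45 + 27 = 72 (Table 5B).
- Candidate cytokines in 2A: 39, with nine cut-offs and so ten categories (models 2A and 2B).
- Tree: depth at most 3, leaf at least 5, complexity parameter 0.01.
- Correlation among cytokines: principal component 1 explains 31.4% of all 39 (Analysis 3, model B). With a common correlation ρ, (1 + 38ρ)/39 = 0.314 gives ρ = (39 × 0.314 − 1)/38 = 0.296.

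**3. Size of the search.** With ordered categories the first node offers up to 39 × 9 = 351 splits. The SAP calls the variables categorical. If the software treats them as unordered, each allows up to 2⁹ − 1 = 511 two-way groupings, so up to 39 × 511 = 19,929.

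**4. Assumptions not in the SAP.** Normal outcome; SD of relative change 5/12.8 = 0.39; responder share 30-50%; patients distributed like controls on the cytokines; at least 15 patients before a node is split; cut-off chosen to maximise sensitivity plus specificity. No cytokine has any effect.

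**5. Tree at complexity parameter 0.01 kept (600 null trials per coding).**

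| | Ordered | Unordered |
|---|---|---|
| Mean apparent AUC | 0.77 | 0.86 |
| 5th-95th percentile | 0.68-0.85 | 0.79-0.93 |
| Trials with AUC ≥ 0.70 | 90% | over 99% |
| Mean sensitivity / specificity | 0.73 / 0.71 | 0.83 / 0.77 |
| Mean PPV / NPV | 0.65 / 0.81 | 0.73 / 0.88 |
| AUC in 2,000 new patients | 0.50 | 0.50 |

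A separate simulation (600 trials, ordered, ρ = 0.33, 30% of variance from seven covariates, responder share about 45%) gave 0.78, with 94% of trials at or above 0.70 and again 0.50 in new patients.

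**6. Tenfold cross-validation used to prune (180 null trials per coding).** The noise tree collapses to no split in 92% (ordered) or 90% (unordered) of trials under the minimum-error rule, and in 99% or 96% under the 1-SE rule. Averaged over all trials the AUC is 0.50-0.52. Where a split survives, the apparent AUC is about 0.68-0.73. In the separate simulation (400 runs, depth 0 to 3 chosen by cross-validation) 82% collapsed, and the apparent AUC was 0.65.

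**7. Analysis 1 for comparison.** Category sizes from Table 5B: 5+3 = 8, 19+9 = 28, 13+6 = 19, 8+9 = 17. With no association (4,000 trials), mean apparent AUC is 0.58 with four fitted levels (1.4% of trials at or above 0.70), 0.57 for the best of the four one-against-rest contrasts, and 0.55 for category 2 against the rest.

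**8. Which correction works (60-80 null trials; true AUC 0.50).** Subtracting bootstrap optimism leaves 0.62 (ordered) and 0.70 (unordered). With the tree regrown in each resample, out-of-bag bootstrap AUC is 0.50 for both codings, and repeated tenfold cross-validation gives 0.48 (ordered) and 0.50 (unordered).

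**The case against.** **Cross-validation is already in the plan.** This is the strongest reply. If the tenfold cross-validation prunes, most noise trees disappear and nothing is left to report. That stands, and it means the inflated result is possible rather than certain. But the SAP names only the fixed complexity parameter, and pruning does not correct the figures of a tree that survives.

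**The heading also says assessing performance, and bootstrapping has its own heading.** True. Reporting apparent performance is legitimate when it is labelled as such. The heading offers both descriptions for figures that meet only the second.

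**Everything is exploratory.** Statistical principles says so, but its remark about confirmation in future studies concerns predictors of treatment effect. Exploratory status does not settle whether validation should depend on the results.

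**Stronger readings a reader might infer.**

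- *That analysis 1 is equally affected.* The SAP does not support this. Under Cytokine profiling the clusters were formed without post-randomisation data, and each category is compared with the other three combined. A yes/no variable of that kind offers no threshold to tune.
- *That objective 2 rests on these AUCs.* It does not. Main analyses names two criteria for each model, R² with and without the variable of interest and the effect size. The ROC measures are supportive, and no decision rule depends on them.
- *That discrimination in 2B would be all noise.* 2B also includes age, leg pain, fear avoidance and other suspected prognostic factors, and it was not simulated. Optimism would be added to whatever real discrimination they bring.

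**Conclusion.** The point holds for analyses 2A and 2B. The plan makes training-set ROC figures mandatory, files them partly under internal validation, and leaves resampling validation to a choice made after the results are known. If the tree at complexity parameter 0.01 is kept, noise alone in 2A would show a mean AUC of about 0.77 to 0.86 where the truth is 0.50. If cross-validation prunes, the problem becomes rare but is not removed, since surviving noise trees still show about 0.65 to 0.73.

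These sizes rest on the simulation assumptions listed, chiefly the outcome SD, the common correlation of about 0.3 and the responder share. Whether the software treats the categories as ordered matters as well, and the SAP does not say.

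The outputs are supportive, so the main hypothesis 2 criteria are outside this point. The change should still be made, because a cut-off with predictive values is easily taken up by readers.

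**What to change.** 1. Under Internal validation, replace the conditional sentence for 2A and 2B by a commitment, for example: *For analyses 2A and 2B we will report out-of-bag bootstrap or repeated cross-validated AUC, sensitivity, specificity, PPV and NPV whatever the results. Tree growing, pruning and choice of cut-off will be repeated in every resample.* Choose one of the two methods in advance. Simple optimism subtraction is not enough for these trees.
2. In model 2, state that the tree is pruned by the tenfold cross-validation and by which rule (minimum error or 1-SE), and that a tree with no split will be reported as such. State whether the cytokine categories are ordered, and the rule for the cut-off.
3. Under Supportive analyses, delete internal validation from the heading and call the uncorrected figures *apparent performance*. Base statements on the prognostic performance of 2A and 2B on the resampled figures.

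Analysis 1 needs only the *apparent performance* label. The cost is SAP wording and computing time, with no new data. The reported discrimination will be less favourable.

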The sample size for the main trial results was calculated to assess the treatment effect separately in each MC type group (1/2). In each MC type group, the study was designed to detect ($\beta = 0.1$, two-sided $\alpha = 0.05$) a mean difference of 4 (SD 5) in the RMDQ score between the two treatment groups (amoxicillin or placebo) at one-year follow-up. In total 180 patients were actually included (intention to treat population), 118 in the MC type 1 group and 62 in the MC type 2 group (16).

The trial protocol gives further details regarding sample size calculation and trial methods (1).

The AIM trial showed a statistically significant – but not clinically important – effect of Amoxicillin in the type 1 MC group, but no effect in the in the type 2 MC group (16). Subgroup analyses indicated a clinically relevant effect in patients with MC related oedema on MRI STIR sequences/series (7) and possibly also a borderline clinically relevant effect in younger patients (aged < 40 years)(6).

Patients

Patients included in this present study were a selected group with as ‘pure’ MC types as possible, who gave consent to participate in the AIM trial, and who provided blood samples and underwent MRI prior to enrolment. Of those selected 78 subjects were eventually randomized and took part in the AIM trial, 6 subjects did not satisfy the AIM eligibility criteria and were not included in the AIM trial (figure 1).

The selection criteria for this present study were, firstly, that two study radiologists agreed that the MRI inclusion criteria of the AIM trial (52) were fulfilled (i.e., type 1 and/or type 2 MCs with height \geq 10% of vertebral body height and diameter > 5 millimeters existed at the level of a prior disc herniation (index level)). Secondly, that type 1 was the most extensive MC type at two or more index level endplates (categorized as MC1, n=47) or that type 2, but not type 1, existed at the index level (categorized as MC2, n=48). From this selected group we included 84 subjects (46 MC1, and 37 MC2) in the present study.

Controls

Statistical Analysis Plan for analysis of cytokines as prognostic factors and predictors of antibiotic treatment effect in patients with chronic low back pain and Modic changes (the AIM trial) - - version 1.0

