To explore potential predictors of treatment effect we will perform six main analyses (1A, 1B, 1C, 2A, 3A, 3B) of predictors of antibiotic treatment effect (Table 2). All six analyses will be performed using multiple regression with RMDQ score at one year as dependent variable and the interaction term (predictor*treatment group) as independent variable adjusted for baseline RMDQ score, the potential predictor, the treatment group, the randomization stratification variables (MC type (1/2) and for former disc herniation surgery (yes/no)).

We will only use the baseline value for any potential predictor of treatment effect and for any covariate. Within each category (subgroup) of categorical variables, we will report the treatment effect predicted in the interaction term analysis by marginalizing (using the margins command in Stata) over the other covariates (and not perform a separate stratified analysis).

We will present results of analyses 1A, 1B, 1C, 2A, 3A and 3B in a forest plot of effect estimates for each potential predictor of treatment effect with 95 % CIs and the p value for the interaction (predictor *treatment group). The overall treatment effect will be marked on the plot (56). The plot will also show the treatment effect within subgroups.

Table 2 –Main analyses of cytokine-defined predictors of treatment effect

| Hypothesis and rationale | Variables and subgroups | Analysis |
|--|---|---|

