-Independence of effect: If the treatment effect (difference in RMDQ score at 1 year follow-up between antibiotic and placebo groups) are more than 4 RMDQ points in any of the main analyses 1(A, B, or C), 2(A), or 3(A or B) we will repeat the same analysis including interaction terms of all such relevant variables x treatment group, age (dichotomized as above or below 40 years) x treatment group and STIR composite variable x treatment group (without the individual covariates age and STIR composite variable) in the same regression analysis (59). Both age and STIR composite variable modified the treatment effect in our prior analyses.

Analyses of cytokines as prognostic factors (hypothesis 2)

For hypothesis 2, we define eleven main analyses (1, 2A, 2B, 3, 4A, 4B, 5A-E) of prognostic factors. These main analyses are ranked in order, from what we consider most to least likely to be prognostic factors (based on prior evidence and knowledge of cytokines).

Main analyses

We will perform linear regression models as main analyses that all will have the following in common:

-Relative change in RMDQ from baseline to one-year follow-up will be dependent variable. This differs from other analyses in the AIM trial (RMDQ at one-year follow-up was dependent variable) because we here consider it problematic to adjust for baseline RMDQ-score as it could induce bias (due to regression to the mean or horse-riding / collider problems) (60). Such adjustment could on the other hand also be highly desirable because baseline score is thought to be one of the most important predictors of future follow-up scores (61, 62). Our choice of dependent variable attempts to take the baseline value into account, while avoiding the possible problem related to adjusting for the baseline value.

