Assess other possible confounders (not included in main analyses due to power limitations):

We will perform a sensitivity analysis for the main analysis (1, 2A and 2B), with the same statistical model but only including covariates with statistically significant beta coefficient in the corresponding main analysis, and depending on available number of further covariates (given maximum eight), the

Statistical Analysis Plan for analysis of cytokines as prognostic factors and predictors of antibiotic treatment effect in patients with chronic low back pain and Modic changes (the AIM trial) - - version 1.0

following covariates will be considered: treatment group (amoxicillin/placebo), comorbidity, NSAIDs use (at baseline and one-year follow-up), physical workload, sleep disturbance(64), BMI, smoking, LBP intensity at baseline (0-10 NRS), and prior surgery for disc herniation. Each sensitivity analysis will be compared to their respective main analysis by assessing R^2 .

The following sensitivity analyses will be considered performed:

Assess the possibility of non-linear effects of the cytokine

For each main analyses 5 (A-E), we will consider using a correspondent multivariable fractional polynomial (MFP) model or other polynomial regression model (73). All covariates of the original regression analyses will be forced included (by setting nominal p-values for variable selection to one in MFP model), only the independent variable of interest will be tested for a non-linear relationship (degrees of freedom for other continuous variables will be set to one) with (for MFP) standard powers (-2, -1, -0.5, 0, 0.5, 1, 2, and 3) and a fractional polynomial election significance level of 5% (using the mfp command in Stata). Each MFP model will be compared to its respective main analysis by assessing R^2 .

Independence of effect:

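### NSAID use at one-year follow-up is listed as a possible confounder of the baseline cytokine association, although it is recorded with the outcome and is probably influenced by it

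*SAP*

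**What the plan says.** The passage is in the SAP's hypothesis 2 section, Supportive and sensitivity analyses, under a subheading that begins "Assess other possible confounders (not included in main analyses due to power limitations". For models 1, 2A and 2B the regression is rerun with only those covariates that were statistically significant in the main analysis. Free places, up to a maximum of eight covariates, may then be filled from a list: "following covariates will be considered: treatment group (amoxicillin/placebo), comorbidity", and further on "NSAIDs use (at baseline and one-year follow-up), physical workload". The same list restricts low back pain intensity to its baseline value. The result is judged by model fit: "Each sensitivity analysis will be compared to their respective main analysis by assessing R^2".

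Three other places fix the timing and the SAP's own standards:

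- **Exposure.** The Patients section describes participants "who provided blood samples and underwent MRI prior to enrolment".
- **Outcome.** The hypothesis 2 Main analyses section states: "Relative change in RMDQ from baseline to one-year follow-up will be dependent variable".
- **Covariates for hypothesis 1.** The Inferential statistics section states: "We will only use the baseline value for any potential predictor of treatment effect and for any covariate". No equivalent sentence is given for hypothesis 2.

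**The concern.** A confounder has to act on, or share a cause with, the exposure. NSAID use a year after the blood sample cannot have influenced the cytokine level in that sample. It is recorded at the time of the outcome, and patients who are more disabled at one year are likely to take more analgesics. Adjusting for it would then partly adjust for the outcome itself.

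This rerun is meant to show whether the cytokine association survives control for further confounders. With this covariate in the model, a shrunken coefficient could be read as evidence of confounding when none exists. The higher R² could be read as a better model when the gain comes from a variable that follows the outcome.

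The SAP is alert to this kind of problem elsewhere. It avoids adjusting for baseline RMDQ in the main models because this "could induce bias (due to regression to the mean or horse-riding / collider problems"), and it plans unadjusted models in case covariates are mediators. It gives no such caution, and no justification, for the one-year NSAID variable.

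**Working it through.** The plan states no figure on this point, so there is none to reproduce. The check has three parts.

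**1. Roles the variable can have.** The order in time is: cytokines C (before enrolment), then one-year RMDQ status Y and one-year NSAID use M (same visit).

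- If Y drives M, M is a consequence of the outcome.
- If C affects M and M affects Y, M is a mediator.
- If C and Y both affect M, M is a collider.

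In none of these is M a confounder. On a purely predictive reading it fails too: objective 2 asks about prognostic value added to known factors, and a value recorded on the outcome date is not available at baseline.

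**2. Direction of the bias.** Take a linear version with higher Y worse: Y = bC + e and M = γY + δC + u, where e and u have variances σe² and σu². Regressing Y on C and M gives

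- coefficient of M: θ = γσe² / (γ²σe² + σu²)
- coefficient of C: b − θ(γb + δ) = b(1 − θγ) − θδ

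Since θγ lies between 0 and 1, the first term shrinks b whenever Y affects M. The second term is the collider part, and it can produce an inverse association when b = 0. If γ = 0 there is no bias.

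**3. Size, by simulation.** The documents give no NSAID prevalence or odds ratios, so those inputs are assumptions.

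*(a) Two groups, RMDQ points.* From the SAP: n = 78, SD 5, and a difference of 4 points, which it equates with its 30% relevance threshold (4 of 12.8). Assumed: equal groups, NSAID use of 40% at mean RMDQ, no confounding, no direct cytokine effect on NSAID use. 4,000 data sets per row.

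| Odds of NSAID use per RMDQ point | Same, per 5 points | Adjusted difference | Attenuation | R² without → with M | Significant, with M |
|---|---|---|---|---|---|
| 1.1 | 1.1⁵ = 1.61 | 3.8 | 5% | 0.15 → 0.20 | 92% |
| 1.2 | 1.2⁵ = 2.49 | 3.4 | 14% | 0.15 → 0.28 | 88% |
| 1.3 | 1.3⁵ = 3.71 | 3.1 | 24% | 0.15 → 0.35 | 85% |

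Without M the difference is significant in about 94% of data sets. With prevalence at 30% or 50% the attenuation stays between 4% and 24%. Set against a mean baseline of 12.8, 3.4 points is 27% and 3.1 points is 24%, both below the 30% threshold that the true difference meets (4/12.8 = 31%).

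*(b) Continuous cytokine.* The SAP's detectable R² increase of 7 percentage points, taken as 7% of outcome variance, corresponds to a standardised slope of √0.07 = 0.265. Assumed prevalence is about 40–44%; 2,000,000 simulated records.

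- Outcome-to-NSAID odds ratio of 1.5, 2, 3 or 5 per SD, no direct cytokine path: the adjusted slope is 0.256, 0.242, 0.217 or 0.190 (3% to 28% attenuation).
- Direct cytokine-to-NSAID odds ratio of 1.5 to 2 added: the slope is between 0.224 and 0.083 (15% to 69% attenuation).
- No true association: slope 0 without the direct path, and −0.035 to −0.123 with it.

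**The case against.** The strongest objection is that little hangs on this. The variable is one optional candidate in a secondary analysis and may never enter a model. No main hypothesis 2 model contains an NSAID variable, and the whole SAP is declared exploratory. The baseline-only rule belongs to hypothesis 1, so no rule is broken. That one-year disability drives NSAID use is plausible but not documented, and concurrent NSAID use might instead lower RMDQ. The odds ratios are invented, and the upper two are strong when expressed per SD. The average shift in simulation (a) is smaller than one sampling SD of the estimate (about 1.1 points), and most data sets remain significant. The simulation also uses RMDQ points, whereas the planned outcome is relative change. Finally, the planned unadjusted models would be reported alongside and cannot be distorted by this covariate.

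Much of this stands. It limits the reach to one sensitivity analysis and makes the figures illustrative. The hypothesis 1 sentence shows a standard the SAP applies elsewhere, not a contradiction. The objection does not rescue the entry. If NSAID use lowers RMDQ, the variable is a mediator or co-intervention, still not a confounder of a baseline measurement. Comparing by R² gives no protection either, because R² rises most when the covariate follows the outcome most closely.

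**Conclusion.** The concern holds. One-year NSAID use does not belong in a list of possible confounders of a baseline cytokine association, and including it would make the robustness check misleading. Under the assumptions shown, the attenuation is about 4% to 24% for a true 4-point difference, with R² rising from 0.15 to between about 0.20 and 0.36 with no confounding present. It is larger, and can create a false inverse association, if cytokines also relate directly to later NSAID use. There is no bias if one-year RMDQ status does not influence NSAID use, or if there is neither a true association nor a direct cytokine path. The main analyses are untouched. Baseline NSAID use is a proper candidate.

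**What to change.** In the hypothesis 2 sensitivity analysis on other possible confounders, remove the one-year value from the NSAID entry so that only baseline use can be considered. It would help to state for hypothesis 2 the baseline-only covariate rule already given for hypothesis 1. If one-year NSAID use is of interest, report it descriptively or in an analysis labelled as mediation, outside the confounder check. Its use as a predictor in the multiple imputation model (Methods to handle missing data) is sound and can stay. The cost is a few deleted words and at most one added sentence; no data collection or main analysis changes.
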